5 SUBJECT WITHDRAWAL FROM THE STUDY

5.1 Criteria for Subject Withdrawal

A subject may withdraw from the study at any time at his/her own request, or may be withdrawn at any time at the discretion of the Investigator or sponsor for safety, behavioral, compliance, or administrative reasons. Reasons for withdrawal may include, but are not limited to:

- Occurrence of a treatment-emergent AE (TEAE) that represents an unacceptable risk to the subject in the judgment of the Investigator
- The subject dies
- If the Investigator determines it would be impossible to continue the study because:
 - the subject won't comply with protocol requirements
 - the subject is lost to follow-up
 - there are technical issues at the site
- If a subject becomes pregnant
- The Investigator determines it is necessary to discontinue the study
- The subject withdraws his or her consent
- The Sponsor discontinues the study at a specific site
- The Sponsor prematurely terminates the study
- If a protocol deviation leads the investigator to judge it difficult for the subject to continue the study
- Any other reason documented by the investigator

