5.2 Procedures for Subject Withdrawal

Subjects may withdraw from the entire study, including follow-up, at any time without penalty and for any reason without prejudice to his or her future medical care. In all cases, the reason(s) for withdrawal, including the primary reason, must be recorded on the electronic case report form (eCRF). If a subject is prematurely withdrawn from the study for any reason, the Investigator must make every effort to perform the evaluations described for the appropriate early withdrawal visit. If a subject withdraws consent and still agrees to undergo a final examination, this will be documented in the eCRF. A subject may also be withdrawn from the study by the Investigator, Sponsor, regulatory authority(ies), or an Institutional Review Board (IRB). Subjects will also be withdrawn if the entire study is terminated prematurely. Withdrawn subjects will not be replaced.

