6.5 Administration

Investigator will administer IP, SI-722 [REDACTED] or placebo [REDACTED] into the subject's bladder via catheter once.

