8.2 Safety Assessments

8.2.1 Adverse Events

- Assessment Points: AE will be reported from Informed Consent to Day 29 or an early withdrawal visit.
- Method: See [Section 10.4](#) for collecting AE information

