9.9 An Early Withdrawal Visit

Subjects who discontinue early from the study will be asked to complete an early withdrawal visit. The following activities will be performed at the early withdrawal visit:

- Perform physical examination
- Record vital signs
- Collect blood sample for laboratory tests (hematology, chemistry and coagulation) and PK
- Collect urine sample for urinalysis, urine culture, and PK
- Perform urine pregnancy test
- Perform cystoscopy
- Record PRO assessments (BPIC-SS, ICSI/PI, and GRA)

- Collect concomitant medication and therapy information
- Review of subject daily diary
- Record AEs

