9.10 Unscheduled Visit

In the event the Investigator needs to conduct follow-up assessments to evaluate an AE, the following safety assessments may be performed on an unscheduled visit:

- Physical examination
- Record vital signs
- Collect blood sample for laboratory tests (hematology and chemistry) and PK if considered appropriate
- Perform cystoscopy, if necessary

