10.4 Process for Collecting Adverse Events and Serious Adverse Events Information

All AEs and SAEs will be collected from the signing of the ICF continuously until Day 29 as specified in the Schedule of Activities (See [Table 1](#)).

Medical occurrences that begin before the start of study treatment but after obtaining informed consent will be recorded on the medical history/current medical conditions section in the eCRF not the AE section.

All SAEs during study treatment period will be recorded and reported to the Sponsor or designee within 24 hours, as indicated in [Appendix 12](#).

The Investigator will submit any updated SAE data to the Sponsor or designee within 24 hours of it being available.

Investigator will conduct physical examination to collect on Screening, Day 1 (pre-dose), Day 2, Day 3, Day 5, Day 8, Day 15 and Day 29 or an early withdrawal visit. Investigators should pay special attention to clinical signs related to previous serious illnesses.

Investigators are not obligated to actively seek AE or SAE reports from former study subjects. However, if the Investigator learns of any SAE, including a death, at any time after a subject has been discharged from the study, and he/she considers the event to be reasonably related to the study treatment or study participation, the Investigator must promptly notify the Sponsor.

The method of recording, evaluating, and assessing causality of AE and SAE and the procedures for completing and transmitting SAE reports are provided in [Appendix 12](#).

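### After the single dose, withdrawal under 5.1 stops no treatment but ends the search for new AEs before Day 29, while the subject stays in the TEAE denominator

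*Combined protocol and SAP*

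**What the plan says.** Section 6.5 has the product put into the "bladder via catheter once". There is no second dose.

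Section 5.1 lists reasons for which a subject may be withdrawn from the study. They include "Occurrence of a treatment-emergent AE (TEAE) that represents an unacceptable risk to the subject in the judgment of the Investigator", failure to comply with the protocol, and "If a protocol deviation leads the investigator to judge it difficult for the subject to continue the study". Section 5.2 adds: "Withdrawn subjects will not be replaced".

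What follows is set in several places:
- Section 9.9: "Subjects who discontinue early from the study will be asked to complete an early withdrawal visit". It covers examination, vital signs, laboratory tests, PK, cystoscopy, questionnaires and AEs. Section 5.2 asks for every effort to hold it. Neither section says when it takes place.
- Section 8.2.1: "AE will be reported from Informed Consent to Day 29 or an early withdrawal visit".
- Section 10.4: "All AEs and SAEs will be collected from the signing of the ICF continuously until Day 29". The sentence then refers to the Schedule of Activities in Table 1, where the last visit column is shared by Week 4 and early withdrawal. Section 10.4 also says that sites need not actively seek AEs from former subjects.
- Sections 10.1 and 10.6 keep the investigator responsible for AEs already known. Section 10.4 requires notice of a related SAE learned of after discharge.

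In the analysis, every dosed subject is in the safety population (11.1.3), TEAEs are given as number and percentage of subjects (11.4.1), and missing data are excluded without imputation (11.6.3).

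**The concern.** In a multiple-dose trial, withdrawal for an AE usually protects the subject by stopping the drug. Here the drug has already been given. The only things left to stop are study procedures, and these can be dropped one at a time. Section 5.1 offers no such intermediate status: the subject leaves the study, and with it the schedule that would bring new events to light.

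Safety and tolerability is a primary objective, and each dose level has 6 active subjects. A dosed subject who leaves early still counts in the TEAE denominator. A new event after exit that nobody asks about is therefore tabulated as no event. A subject withdrawn for a TEAE is also one who tolerated the dose badly, whose later course is of particular interest. Later PK samples, questionnaires and diary entries are lost as well.

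**Working it through.** **Inputs from the protocol.** Four cohorts randomized 6:2 (3.2, 3.5): 4 × 6 = 24 active and 4 × 2 = 8 placebo, total 32, which matches 3.4. Placebo is pooled (11.6). Follow-up runs to Day 29, which is 28 days after the dosing day. There are 14 post-dose PK blood samples, of which 48, 96, 168, 336 and 672 h fall on Days 3, 5, 8, 15 and 29 (8.1.1, Table 1). After dosing, BPIC-SS and GRA are due on Days 8, 15 and 29 (8.3.2). The Safety Review Committee (SRC) reviews data through Day 8 at a minimum (6.8).

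**Assumptions.** The documents give no exit day, withdrawal rate or late-AE rate. Ranges are shown for each.

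**1. What one early exit leaves uncovered.** With the exit visit on Day d, the days without an active search for new AEs are 29 − d. Of these, max(0, 8 − d) fall within the SRC's Day 8 data.

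| Exit visit on | Days without search (of 28) | Of which up to Day 8 | Later PK times (of 14) | Later BPIC-SS/GRA times (of 3) |
|---|---|---|---|---|
| Day 3 | 26 (93%) | 5 | 4 | 3 |
| Day 5 | 24 (86%) | 3 | 3 | 3 |
| Day 8 | 21 (75%) | 0 | 2 | 2 |
| Day 15 | 14 (50%) | 0 | 1 | 1 |

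For exit on Day 3 or 5, the exit visit itself supplies one off-schedule questionnaire reading.

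**2. Effect of one missed event on incidence.** If the subject had no earlier event of that term, the percentage falls by 1/6 = 16.7 points in an active cohort or 1/8 = 12.5 points in pooled placebo.

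**3. How often this could arise.** Let w be the proportion of dosed subjects withdrawn for these reasons. The expected number is 32w, and the chance that a given active cohort has at least one is 1 − (1 − w)^6.
- w = 2%: 0.6 subjects; 11%
- w = 5%: 1.6 subjects; 26%
- w = 10%: 3.2 subjects; 47%

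**4. Chance of seeing a late AE at least once in a cohort of 6.** Let p be the true rate of an AE that starts after the exit time. With all 6 followed, the chance is 1 − (1 − p)^6. Averaged over withdrawal, with no post-exit event detected, it is 1 − (1 − p(1 − w))^6.

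| p | All 6 followed | w = 2% | w = 5% | w = 10% |
|---|---|---|---|---|
| 10% | 46.9% | 46.1% (−0.7) | 45.1% (−1.8) | 43.2% (−3.6) |
| 20% | 73.8% | 73.0% (−0.8) | 71.8% (−2.0) | 69.6% (−4.2) |
| 30% | 88.2% | 87.6% (−0.6) | 86.6% (−1.6) | 84.9% (−3.4) |

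If one of the 6 is known to have left, the chance is 1 − (1 − p)^5 = 41.0%, 67.2% or 83.2%, a loss of 5.9, 6.6 or 5.0 points. That is the loss in an affected cohort; the table gives the loss expected in advance.

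**The case against.** **Section 5.1 is permissive and its thresholds are high.** A TEAE has to be an unacceptable risk, and non-compliance has to make continuing impossible. The remaining schedule includes cystoscopy on Days 8 and 29 and repeated blood draws, so withdrawal can serve safety even with no drug to stop. This stands. But nothing tells the investigator to keep a dosed subject in follow-up, and no option is given to drop only the risky procedure.

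**A subject withdrawn for a TEAE has a known AE and will be in contact with the site.** Section 10.6 requires proactive follow-up after an AE report, and under 9.10 "the following safety assessments may be performed on an unscheduled visit". New events may well surface that way. This narrows the gap and rules out saying that withdrawal ends all observation. The safeguards still attach to events already known or volunteered. None requires a search for new ones, and no contact is scheduled after exit.

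**A reader might infer that 8.2.1 and 10.4 contradict each other**, so that some sites would stop at exit and others continue to Day 29. The documents do not support this. The Day 29 sentence in 10.4 defers to Table 1, whose last column also serves early withdrawal, and the former-subject sentence points the same way. Read together, the sections stop collection at exit; the wording of 10.4 is only loose.

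**Other text hints that follow-up can outlast withdrawal.** Section 5.2 speaks of leaving the entire study including follow-up, and 6.7 tells unblinded, withdrawn subjects to complete follow-up procedures. The first defines no lesser form of withdrawal. The second may mean only the exit visit and concerns only unblinded subjects.

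**The analyses are descriptive and the expected loss is small.** Both are true, and they limit the weight of the point. Section 11 leaves data handling to the SAP, but no analysis can recover events that were never sought.

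**Conclusion.** The point holds as a gap in follow-up. After the single instillation, withdrawal for a TEAE, non-compliance or a deviation ends scheduled assessments and the active search for new AEs at an exit visit of unspecified timing, while the subject remains in the denominator. Late TEAE incidence can be understated as a result.

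For an affected cohort the effect can be visible, since one unsought event is a sixth of the active subjects. Averaged in advance it is modest: at most about 4 points of detection probability over the assumed ranges, and under 1 point at a 2% withdrawal rate. Those figures assume that no post-exit event is detected, so they are upper values for a given w and p. SRC data are affected only by exits before Day 8.

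A reader might also infer a bias between active and placebo. Its direction is unknown, because the documents give no basis for saying which arm would lose more subjects. The change is worth making because it is cheap and bears on a primary objective, not because the expected loss is large.

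**What to change.** In 5.1 and 5.2, state that once a subject has been dosed, a TEAE, non-compliance or a deviation does not by itself end follow-up. The subject continues the scheduled assessments to Day 29 while consent and contact hold. If a particular procedure is judged unsafe, for example cystoscopy, only that procedure is omitted.

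At minimum, amend 8.2.1 and the former-subject sentence of 10.4 so that AEs are actively collected to Day 29, by phone if needed, from withdrawn dosed subjects who still consent. Section 18.3 already provides a model for collecting AEs and questionnaires by phone. It classes those COVID-19 phone visits as deviations, so the new text should say that these calls are planned contacts and not deviations.

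The cost is amendment wording and a few contacts per withdrawn subject, with no new subjects or procedures. The downside is some partial data, and little gain from subjects who will not comply at all.

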5.2 Procedures for Subject Withdrawal

Subjects may withdraw from the entire study, including follow-up, at any time without penalty and for any reason without prejudice to his or her future medical care. In all cases, the reason(s) for withdrawal, including the primary reason, must be recorded on the electronic case report form (eCRF). If a subject is prematurely withdrawn from the study for any reason, the Investigator must make every effort to perform the evaluations described for the appropriate early withdrawal visit. If a subject withdraws consent and still agrees to undergo a final examination, this will be documented in the eCRF. A subject may also be withdrawn from the study by the Investigator, Sponsor, regulatory authority(ies), or an Institutional Review Board (IRB). Subjects will also be withdrawn if the entire study is terminated prematurely. Withdrawn subjects will not be replaced.

5.3 Lost to Follow-up

A subject will be considered lost to follow-up if he or she repeatedly fails to return for scheduled visits and is unable to be contacted by the study site.

The following actions must be taken if a subject fails to return to the clinic for a required study visit:

- The site must attempt to contact the subject and reschedule the missed visit as soon as possible and counsel the subject on the importance of maintaining the assigned visit schedule and ascertain whether or not the subject wishes to and/or should continue in the study.
- Before a subject is deemed lost to follow-up, the Investigator or designee must make every effort to regain contact with the subject (where possible, 3 telephone calls and, if necessary, a certified letter to the subject's last known mailing address or local equivalent methods). These contact attempts should be documented in the subject's medical record.
- Should the subject continue to be unreachable, he/she will be considered to have withdrawn from the study with a primary reason of lost to follow-up.

6 STUDY METHOD AND PROCEDURES

6.1 Informed Consent

Before each subject is enrolled to the study, informed consent, using a form approved by the IRB responsible for that site, will be obtained from the subject according to the regulatory and legal requirements of the participating country/state. This consent form must be signed, dated, and retained by the Investigator as part of the study records. The Investigator will not undertake any investigation specifically required only for the clinical study until valid consent has been obtained. When consent is obtained must also be documented in the subject source record and eCRF.

If a protocol amendment is required, the ICF may need to be revised to reflect the changes to the protocol. If the ICF is revised, it must be reviewed and approved by the appropriate IRB and signed by all subjects subsequently enrolled in the study as well as those currently enrolled in the study, except for when the change is administrative or resigning is not required per the IRB. If the IB is updated during the study or new risks/information becomes available, ICF will need to be updated and new form signed by subjects still in study or entering study.

6.1.1 Subject Identification

At the screening visit, a unique subject number will be assigned consecutively for each subject after he or she signs the ICF. Subjects who drop out of the study before randomization will retain their unique subject number (ie, the subject number will not be reassigned). If a subject is rescreened after being designated as a screen failure, the subject will receive a new unique subject number upon rescreening.

6.2 Subject Entry

At the time of each subject's entry into the study, the investigator will perform all the examinations described in [Table 1](#) and confirm that the subject is eligible for the study. Each subject who is judged as eligible for the study by the Investigator will be enrolled into the study.

6.3 Screen Failure

Screen failures are defined as subjects who consent to participate in the clinical study but are not subsequently randomized in the study. A minimal set of screen failure information is required to ensure transparent reporting of screen failure subjects to meet the Consolidated Standards of Reporting Trials (CONSORT) publishing requirements and to respond to queries from regulatory authorities. Minimal information includes demographics and reason for screen failure.

6.4 Re-screening

Re-screening of subjects may be allowed if the reason for screen failure is any of the following Inclusion and Exclusion Criteria:

Inclusion Criteria 3

Exclusion Criteria 2, 5, 6, 7, 8, 9, 10, 11, 12, 14, 15, 17, 21 and 25

Additionally, re-screening of subjects who were screened but were not dosed because of cohort closing may be allowed.

6.5 Administration

Investigator will administer IP, SI-722 [REDACTED] or placebo [REDACTED] into the subject's bladder via catheter once.

6.6 Blinding

The Investigator, site personnel, and subjects will be blinded to the study treatment. Subjects will be randomly assigned in a 6:2 ratio to receive SI-722 or placebo, respectively. Investigators will remain blinded from each participant's assigned study treatment throughout the course of the study. In order to maintain this blind, the investigational drug will be prepared by an appropriate unblinded staff not otherwise involved in the study to ensure the blinding. In the event of a Quality Assurance audit, the auditor(s) will be allowed access to unblinded study treatment records at the site(s) to verify that randomization/dispensing has been done accurately.

6.7 Unblinding

All subjects, site personnel, and Investigators involved with the conduct of the study (except for an unblinded staff) will be blinded with regard to study treatment assignments. The blind may be broken in exceptional circumstances. In a medical emergency, when the management of a subject's condition requires knowledge of the treatment assignment, the Investigator, or designee, will obtain the study treatment assignment through Interactive Response Technology (IRT). The medical emergency should be discussed with the medical monitor prior to obtaining the treatment assignment, or as soon after as possible.

If the randomization code for a subject is broken, the Investigator will record the date and reason for breaking the blind for that subject in the source documents. Upon unblinding, the subject will be withdrawn from the study and should complete all follow-up procedures.

Unblinded study staff will examine and reconcile study medication orders, records of receipts, dispensing records, and inventory forms throughout the study.

6.8 Safety Review Committee

An unblinded SRC will evaluate the safety, tolerability and PK of SI-722 1 week after administration for each cohort before advancing to the next higher dose.

After administration for each cohort is completed, the SRC will review and assess (at a minimum) safety, tolerability and PK data through Day 8 prior to dose escalation for the next cohort of subjects. The SRC will carefully evaluate the propriety of continuing to focus on urologic-related adverse events (AEs). Prior to each SRC meeting, an interim blinded safety report will be prepared for that cohort presenting the relevant safety and tolerability findings.

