Outpatient visit	X													X	X	X	X	
Inpatient confinement			Day 1 through Day 2															
Medical history	X																	
IC/BPS history	X																	
Review of inclusion/exclusion criteria	X		X															
Physical examination	X		X										X	X	X	X	X	
Gynecologic examination	X																	
Height, Body weight, Demographics	X																	
Serology	X																	
TB blood test	X																	
NAAT	X																	
Urine drug screen	X																	
Hematology	X		X										X	X	X	X	X	
Coagulation	X		X										X	X	X	X	X	
Clinical chemistry	X		X										X	X	X	X	X	
Urinalysis	X		X										X	X	X	X	X	
Urine culture	X																X	
Serum pregnancy test	X																	
Urine pregnancy test			X														X	
Vital signs	X		X				X						X	X	X	X	X	
12-lead ECG			X				X						X					
Cystoscopy			X												X		X	
Distribute subject daily diary	X		X										X	X	X	X	X	
Distribute acetaminophen	X		X										X	X	X	X	X	

Phase	Screening		Double-Blind Treatment Period																		
	1	-	2						3			4		5	6	7					
Visit	1	-	2																		
Week	-4 to -1	-	0												1	2					
Day	-28 to -7	-7 to 1	1						2		3		5		8		15				
Hour			Pre-dose	0	0.25	0.5	1	2	4	6	8	12	24	48	96	168	336	672			
Window				+/- 3 min	+/- 3 min	+/- 5 min	+/- 5 min	+/- 5 min	+/- 5 min	+/- 5 min	+/- 5 min	+/- 5 min	+/- 6 h	+/- 1 D	+/- 1 D	+/- 3 D	+/- 3 D				
Randomization			X																		
IP administration				X																	
PK blood sample collection			X		X	X	X	X	X	X	X	X	X	X	X	X	X				
PK urine sample collection ^a			X		Continuous								X	X	X	X					
Voiding volume record ^b		X		Continuous										X	X	X					
Voiding time record ^c				X																	
BPIC-SS	X		X											X	X	X					
ICSI/PI			X													X					
GRA														X	X	X					
BS-POP	X																				
Subject Daily Diary ^d					Continuous																
Adverse events					Continuous																
Concomitant medications					Continuous																

^a Urine void sample on Day 1 (pre-dose) will be collected at least once. Urine void samples within 30 minutes after study treatment instillation will be included. After each urine sample collection, voiding volume will be recorded.

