3.5 Randomization

Randomization will be utilized to minimize bias in study evaluations. On Day 1, subjects will be randomized to SI-722 or placebo in a 6:2 ratio within four treatment cohorts.

Cohorts will be filled sequentially as subjects are determined to be eligible during Screening. An unblinded Safety Review Committee (SRC) will evaluate the safety and tolerability of SI-722 1 week after administration for each cohort before advancing to the next higher dose.

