8.2.6 Clinical Laboratory Assessments

- Assessment Points: Blood and urine samples for clinical laboratory tests (blood: hematology, coagulation and clinical chemistry, urine: urinalysis) will be collected at Screening, pre-dose on Day 1, Day 2, Day 3, Day 5, Day 8, Day 15 and Day 29 or early withdrawal.

Serology (HIV antibodies, HBsAg, and HCV antibody), TB blood test, Nucleic acid amplification testing (NAAT) for *Neisseria. gonorrhoeae* and *Chlamydia. trachomatis* and Urine drug screen will be done at Screening only.

Pregnancy tests will be done at Screening (serum), pre-dose on Day 1 (urine), and on Day 29 or early withdrawal (urine). Urine culture will be done at Screening, and on Day 29 or early withdrawal.

- Method: The Investigator must review the laboratory report, document this review, and record any clinically relevant changes occurring during the study in the AE section in the eCRF. The laboratory reports must be filed with the source documents. All laboratory tests with values considered clinically significantly abnormal during participation in the study should be repeated until the values return to normal or baseline, or are no longer considered clinically significant by the Investigator, or are otherwise explained and any appropriate action taken.
 - If such values do not return to normal/baseline within a period of time judged reasonable by the Investigator, the etiology should be identified and the Sponsor notified.

- All protocol-required laboratory assessments, as defined in [Appendix 1](#), must be conducted in accordance with the laboratory manual and the Schedule of Activities (see [Table 1](#)).
- If laboratory values from non-protocol specified laboratory assessments performed at the institution's local laboratory require a change in subject management or are considered clinically significant by the Investigator (eg, serious AE [SAE], AE, or dose modification), then the results must be recorded in the eCRF.

Immediate safety concerns should be discussed with the medical monitor upon occurrence or awareness to determine if the subject should discontinue study treatment (See [Appendix 1](#)).

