10.7 Regulatory Reporting Requirements for Serious Adverse Events

Prompt notification (within 24 hours) by the Investigator to the Sponsor of a SAE is essential so that legal obligations and ethical responsibilities towards the safety of subjects and the safety of a study treatment under clinical investigation are met.

The Sponsor has a legal responsibility to notify both the local regulatory authority and other regulatory agencies about the safety of a study treatment under clinical investigation. The Sponsor will comply with country-specific regulatory requirements relating to safety reporting to the regulatory authority, IRB, and Investigators.

Investigator safety reports must be prepared for suspected unexpected serious adverse reactions according to local regulatory requirements and Sponsor policy and forwarded to Investigators as necessary.

An Investigator who receives an Investigator safety report describing a SAE or other specific safety information (eg, summary or listing of SAEs) from the Sponsor will review and then file it along with the Investigator's Brochure and will notify the IRB, if appropriate according to local requirements.

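### The SRC is scheduled to meet only after a whole cohort has been dosed, and no rule requires dosing to pause within a cohort after a related SAE

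*Combined protocol and SAP*

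**What the plan says.** Section 3.5 places the unblinded SRC evaluation "1 week after administration for each cohort before advancing to the next higher dose". Section 6.8 repeats that timing and defines the data cut: "After administration for each cohort is completed, the SRC will review and assess (at a minimum) safety, tolerability and PK data through Day 8". The words in brackets widen the data reviewed; they do not add a meeting. Neither section describes a triggered or ad hoc SRC meeting, a sentinel subject or a minimum gap between doses. Cohorts fill as subjects qualify. Each of the four cohorts is randomised 6:2.

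Other provisions bear on the point:

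- Section 10.4: "All SAEs during study treatment period will be recorded and reported to the Sponsor or designee within 24 hours". Section 10.7 adds: "Prompt notification (within 24 hours) by the Investigator to the Sponsor of a SAE is essential". Neither attaches any action on dosing.
- Section 8.2.6: "Immediate safety concerns should be discussed with the medical monitor upon occurrence or awareness to determine if the subject should discontinue study treatment". The question put to the monitor concerns the affected subject.
- Section 5.1 lists "The Sponsor prematurely terminates the study" among reasons for withdrawal and also allows the investigator to discontinue the study. No trigger is given for either.
- Section 6.8 on urologic events: "The SRC will carefully evaluate the propriety of continuing to focus on urologic-related adverse events". This belongs to the scheduled review.
- Table 1 confines subjects to the unit from "Day 1 through Day 2".
- Section 12.2 allows a change that removes an immediate hazard to be made ahead of IRB approval. Section 6.1 requires an updated consent form when new risks emerge. Section 5.2 lets an IRB or regulator withdraw a subject.
- Section 1.3.1 reports that Phase 1 raised no major safety concern and saw no urinary event that was severe or serious.

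**The concern.** Safety and tolerability is a primary objective. The only completed clinical study described was in healthy subjects (section 1.1), and this is the first to look at efficacy in IC/BPS (section 1.3.2). Suppose the first subject in a cohort has a related SAE. Under the plan as written, the other seven can be dosed before the SRC is due to meet, unless someone chooses to intervene.

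Investigators are blinded (section 6.6), and the SRC is the only body the protocol describes as reviewing safety unblinded. So the group best placed to separate a drug effect from a placebo or procedural event is not convened while the cohort is open. Because each subject receives one instillation, deciding whether the affected subject should stop treatment (section 8.2.6) does nothing for the next subject. Sections 5.1 and 6.6 allow for more than one site, so caution at one site need not reach another.

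**Working it through.** **Design figures.** 4 cohorts × (6 + 2) = 32 subjects; 4 × 6 = 24 on SI-722; 4 × 2 = 8 on placebo. This reproduces section 3.4 and gives 8 subjects per cohort.

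**Worst case.** A related SAE in the first subject leaves 7 undosed. If that subject was on SI-722, 5 of the 7 are assigned to SI-722. With a true related-SAE rate p (assumed; the documents give none), the chance of at least one more among those 5 is 1 − (1 − p)^5: 22.6% at p = 5%, 41.0% at 10%, 67.2% at 20%.

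**Average case.** Take one related SAE on SI-722, equally likely at positions k = 1 to 8 and known before the next dose. The mean number undosed is (7 + 6 + … + 0)/8 = 28/8 = 3.5. The other seven subjects are 5 active and 2 placebo in random order, so 3.5 × 5/7 = 2.5 are assigned to SI-722.

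**Allowing for reporting time.** The dosing pace is not stated, so I bracketed it from the planned period in the synopsis (November 2019 through March 2021). From 1 November 2019 to 31 March 2021 is 516 days; less 28 for screening and 28 for follow-up, 460 remain. There are 4 × 7 = 28 within-cohort gaps and 3 SRC gaps of G days. If dosing fills a share f of the 460 days, the interval is d = (460f − 3G)/28. With a lag of L days from dose to report, the mean undosed is the average over k of max(8 − k − floor(L/d), 0). The values of f, G and L are assumptions.

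| f | G (days) | d (days) | Undosed, L = 2 | Undosed, L = 7 |
|---|---|---|---|---|
| 1 | 7 | 15.7 | 3.5 | 3.5 |
| 1 | 30 | 13.2 | 3.5 | 3.5 |
| 0.5 | 7 | 7.5 | 3.5 | 3.5 |
| 0.5 | 30 | 5.0 | 3.5 | 2.6 |
| 0.25 | 7 | 3.4 | 3.5 | 1.9 |
| 0.25 | 30 | 0.9 | 1.9 | 0 |

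Multiplying by 5/7 gives the SI-722 share: 3.5 becomes 2.5, 2.6 becomes 1.9, and 1.9 becomes 1.3.

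**How often a hold would occur.** At an assumed 1% related-SAE rate on SI-722 and none on placebo: 1 − 0.99^6 = 5.9% of cohorts and 1 − 0.99^24 = 21.4% of trials. With 1% on placebo as well, since placebo subjects have the same catheter and cystoscopy: 1 − 0.99^8 = 7.7% and 1 − 0.99^32 = 27.5%. At a 5% rate on SI-722 only: 1 − 0.95^6 = 26% of cohorts.

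**The case against.** The strongest reply is that the sponsor already has the information and the authority. SAEs arrive within 24 hours, section 5.1 allows the study to be stopped, section 12.2 allows urgent changes before IRB approval, and section 6.1 requires new risks to reach subjects entering the study. Phase 1 was clean for severe and serious urinary events, and each subject has one instillation with an overnight stay. All of this stands, and it lowers the weight of the point. It does not close the gap, because each provision is a reporting duty or a discretionary power and none obliges anyone to hold the next dose.

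A reader might infer that the plan cannot stop dosing, or that escalation is unprotected. The documents support neither. Discretionary stopping exists, and each step up in dose already requires unblinded SRC review.

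A reader might also want the hold extended to severe but non-serious events. The documents give no rates to justify that. Appendix 12 lets a temporal relationship count as related, so catheter and cystoscopy events could qualify. Suppose two related severe events also trigger a hold. With 6 active subjects (SAE probability s, severe t, r = 1 − s − t) and 2 placebo subjects (severe q), the hold probability is 1 − r^6(1 − q)^2 − 6t·r^5(1 − q)^2 − r^6·2q(1 − q). At assumed values s = 1% and t = q = 20%, where the drug adds no severe events, this is 53% of cohorts, and 1 − 0.47^4 = 95% of trials. That trade-off is the sponsor's to weigh and is not part of this point.

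Finally, doses are redacted, as is a line after the sample size in section 3.4, and an SRC charter could hold a rule. The readable text mentions no charter.

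**Conclusion.** The point holds as a precaution worth adopting. SRC review is scheduled only after a cohort is fully dosed, and no readable provision requires a within-cohort pause after a related SAE. A hold would find on average 3.5 subjects still undosed, about 2.5 of them assigned to SI-722, with a range of 0 to 7 in total. This assumes one related SAE on SI-722, equally likely at any position and known before the next dose. The benefit shrinks as dosing speeds up relative to reporting and reaches zero at a 0.9-day interval with a 7-day lag. The gap itself depends on none of these assumptions. The finding should not be read as evidence that SI-722 is unsafe: the only clinical safety data the protocol describes are reassuring, and because doses are redacted it cannot be seen whether they exceed those used in Phase 1.

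**What to change.** Add to section 6.8, with a cross-reference in section 3.5:

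> *If any subject in the open cohort has an SAE assessed as related, further randomisation and dosing at all sites are suspended until an ad hoc SRC meeting has reviewed the event unblinded; the SRC may resume, modify or stop dosing.*

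In section 6.4, add *or a dosing hold* to the allowance for re-screening subjects left undosed when a cohort closes, because a hold may carry screened subjects past the 28-day window. The wording does not rely on the IRT, which the protocol mentions only for emergency unblinding (section 6.7). If an SRC charter already contains this rule, a cross-reference to it in 6.8 is enough.

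The cost is a short amendment with IRB approval, one SRC meeting per hold, and some delay and re-screening. The hold adds no subjects or cohorts and uses the existing SRC and 24-hour SAE reporting. Some holds will be ones that the SRC then lifts; at an assumed 1% related-SAE rate they stay within the 6% to 7.7% of cohorts and 21% to 27.5% of trials worked out above.
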